Short version of the final protocol

(Ver 6, Aug 31, 2018)

Introduction

Every year more than 250,000 patients are admitted in the Capital Region of Denmark. During admissions, the clinical track and trigger system "Early Warning Score (EWS)" is used to systematically observe and detect acutely deteriorating patients. The system is designed to prevent serious adverse events like unanticipated transfer to the intensive care unit, cardiac arrest and unexpected death. EWS consists of standardized measurements of the patient's vital signs and an escalation protocol that determines further actions based on the aggregated EWS score. At admission, and as a minimum twice a day, nurses measure vital signs on all hospitalized patients. Depending on the predetermined cut-off values (i.e. heart rate above 150 bpm = 3 points) an aggregated score is calculated. Based on the total score, the escalation protocol determines the time interval for the next measurement as well as a clinical action (i.e. call for attending doctor). EWS is developed to detect and to treat potentially deterioration of disease that might lead to critical illness and death. In its current form, there is only limited room for individual clinical assessment. A standardized track and trigger system like EWS does not differentiate between different types of disease or the patient's individual physiological response. Therefore, there is a potential risk that the system fails to detect a patient with an abnormal stress response. Additionally; patients suffering from chronic illness might have different normal values than healthy patients, leading to unnecessarily excess observation, measurement, and suboptimal usage of limited staff resources.

Further improvement and optimizing of the EWS track and trigger system is necessary, as there is potential to improve patient care and use staff resources more appropriate. The current study will examine the effect of a new Individual EWS (I-EWS) with incorporated clinical assessment using the staff's professional experience and providing even more personalized observation and treatment.

Aim of the study

The aim of the study is to investigate the impact of the I-EWS that has a systematic involvement of clinical assessment and the possibility to adjust the score, whilst keeping the same escalation protocol. I-EWS will be compared to the existing EWS with a focus on mortality, critical illness, and the use of staff resources.

Hypothesis

The main hypothesis is that I-EWS will be non-inferior to the existing NEWS algorithm regarding 30-day mortality, but the introduction of clinical assessment results in fewer I-EWS scores per patient per day than with NEWS.

Method

The study is a prospective, cluster randomized, cross-over, non-inferiority study. The participating eight hospitals are randomly assigned to six and a half months with either I-EWS or the existing EWS track and trigger system. Computer generated numbers are used to randomize the hospitals to either the intervention or control arm of the study. A single cross-over will take place resulting in a total study period of 13 months. I-EWS is only available at hospitals assigned to I-EWS (Grey areas in the figure below). All EWS scores and subsequent actions are documented in real time. Each period will start with 14 days of implementation, and before cross-over patients will be followed by an observation period of 30 days (indicated by shaded areas below).

Hospital	1 period: 6 ½ months	2. period: 6 ½ months
Herlev & Gentofte Hospital (2 units)	Cluster 1	Cluster 1
Amager og Hvidovre Hospital (2 unit)	Cluster 2	Cluster 2
Nordsjællands Hospital (2 units)	Cluster 3	Cluster 3
Bispebjerg Hospital (1 unit)	Cluster 4	Cluster 4
Glostrup Hospital (1 unit)	Cluster 5	Cluster 5
Sjællands Universitetshospital (2 units)	Cluster 6	Cluster 6
Slagelse Hospital (1 unit)	Cluster 7	Cluster 7
Holbæk Hospital (1 unit)	Cluster 8	Cluster 8

Intervention: Prior to project start ambassadors from all the participating wards will receive 2 hours of education depending on which EWS their hospital is randomized to use. Hospitals randomized to use I-EWS will receive an introduction course and hospitals using EWS will receive a brush-up course. Subsequently, they will be responsible for teaching at their respective wards. I-EWS, like the current EWS, will apply systematic observation, where patients continue to be evaluated according to vital signs and assigned a score of 0-20. The innovation in I-EWS is that SP systematically calls for staff to reassess the assigned score after they have entered the patient's vital signs. Afterwards it is possible to adjust the score by a maximum of +6 or -4. Nursing staff reevaluate when vital signs and clinical assessment are compared, whether the patient is in the correct observation range, and if the clinical actions defined for this range is relevant.

Ethics

The trial was presented to the Regional Ethics Committee, who decided that no formal approval was needed in accordance with Danish law (J.nr. 1701733). The Danish Data protection agency has approved the project. The trial will be registered at clinicaltrials.gov.

Existing workflows are utilized as well as I-EWS is built into SP, so we do not expect the personal to experience a higher workload. When the possibility to individually adjust the observational frequency is given, there is a risk of overlooking critical illness. Therefore, the study only allows a reduction of maximum four points. When carried out, this means that a high EWS score will still trigger more frequent observation. The overall ethical assessment is that the study is safe. As

observed in previous research (publication under review) the introduction of clinical assessment when using triage have improved the risk evaluation in emergency patients, therefore we do not expect that the study will bring along a higher risk for the hospitalized patient.

Statistical analysis plan

Sep 18, 2018, (revised July 11, 2019)

This document contains the statistical analysis plan for the I-EWS study. The statistical analysis plan has been completed prior to the availability of the outcome data and aims to clarify the analyses.

Time line

The study will start at October 1, 2018. Due to implementation patients will be enrolled at October 15, 2018 with planned end of inclusion after one year, October 1, 2019. Follow-up will be concluded on November 1, 2019. The primary analysis will be conducted when the last patient has been followed for 30 days and data is available, which is expected to be Jan 2020.

Background

The primary research question is: A New EWS algorithm (I-EWS) that systematically incorporate clinical assessment, allowing nurses to adjust the I-EWS score will be non-inferior to the existing EWS algorithm and lead to fewer unnecessary EWS measurements, allowing a better utilisation of limited resources.

The study is a cluster-randomized cross-over multi-centre controlled interventional trial conducted at eight large hospitals.

Inclusion/Exclusion criteria

Eligible hospitals

- 1. Located in the Capital Region or Region Zealand I Denmark
- 2. Arrival of acutely admitted patients in on-site Emergency department
- 3. Systemised use of Early Earning Score (EWS) on patients admitted
- 4. Access to Medical Emergency Team
- 5. Access to Intensive Care Units (ICU)

Patient inclusion criteria

- 1. ≥18 years at admittance at participating hospital
- 2. Admittance in a department/Ward using systematised EWS
- 3. Admittance for more than 24 hours

Patients will be included at the first admission in the study period (index admission) and will remain in this group (intervention/control) for a follow-up period of 30 days. All subsequent admissions (readmissions) will be ignored.

Exclusion

- 1. Patients arriving at the gynaecological-, obstetric-, and paediatric department
- 2. If a "do not resuscitate"-order or "no NEWS/I-EWS registration" are identified, patients will be excluded for further analysis at the time of registration.

Definition of clusters

Eligible hospitals can consist of one or two units. A hospital is defined based on its administrative organisation and catchment area. Each hospital will generate one cluster and two (time) periods (control and intervention). See schematic figure 1 below

Randomisation

Prior to the study start participating clusters will be randomised to start as either intervention or control. Eight cluster will be available, and we will be using stratified randomisation based on size of hospitals (number of unique admissions, more than 25,000 admissions is defined as large hospitals, less than 25,000 is small hospitals), to balance a potential size difference between the intervention and control group. The randomization will be performed using computer-generated numbers. The randomisation will allocate participating hospitals to periods of intervention or control in a 1:1 ration. A cross-over will occur after 6.5 months and is expected to be at April 15, 2019.

Ethics

The study was presented to the Regional Ethics Committee, who decided that no formal approval was needed in accordance with Danish law (J.nr. 1701733). Data management has been approved by the Danish Data Protection Agency (ID: HGH-2017-116, I-suite:06030).

Study variables:

The following data are collected as a minimum for the included patients:

- Age and gender
- Personal Identification number (Danish Civil Registration number (CPR)

- Presence of Do Not Resuscitate (DNR) order
- Presence of "No EWS registration"
- EWS/I-EWS Scores
- Registered actions to the EWS/I-EWS escalation protocol
 - Responsible nurse contacted
 - Treatment plan already made
 - Doctor contacted
 - MET contacted
 - Other
 - Charlson Comorbidity Index

At follow-up (30 days after inclusion of last patient) the following data is collected from the National Patient Registry (NPR) and the electronic patient journal system Sundhedsplatformen:

- Contacts with the hospital system (including all historical contacts).
- Information regarding admissions (date, time and place of admission and discharge).
- Diagnoses (follow-up during study period, historical and in relation to index admission).
- Date of death or emigration (only very few cases of emigration are expected).

Sundhedsplatformen, hospital based local databases, and clinical databases (such as DANARREST) will provide data on:

- Registered Cardiac arrest
- MET activation

Endpoints

The primary endpoint;

• All-cause mortality at 30 days

Co-primary endpoint;

• The number of NEWS/I-EWS scores per patient per day

The secondary endpoints;

- Length of hospital stay
- All-cause mortality at 2 days

• All-cause mortality at 7 days

Additionally, the following will be reported;

Use of EWS / I-EWS;

- Frequency of changes in I-EWS scores that lead to an escalation or de-escalation in the escalation protocol
- Comparison of changes in EWS score due to I-EWS modification (intervention group) and due to temporary or chronic acceptable values (control group)
- The number of Cardiac arrests* during hospital stay, reported in numbers (%) and per 10,000 ward days
- Scores generating a call for Mobile Emergency team (MET) reported in absolute number (%) and per 10,000 ward days
- Scores generating calls for the attending doctor, reported in absolute number (%) and per 10,000 ward days

*Definition – Presence of a clinical cardiac arrest (as defined in the resuscitation guidelines) in patients without a DNAR (Do Not Attempt Resuscitation) order. Registered in DANARREST.

Sample size calculation

The study is designed as a non-inferiority study to show that I-EWS is not inferior to the existing EWS algorithm with a non-inferiority margin (Δ) of 0.5% regarding 30-day all-cause mortality. The participating hospitals will admit 189,000 individual patients within one-year, individual sizes (admissions) are described on p.12. The sample size is based on the following assumptions: I) within a the inclusion period of ten months, the participating hospitals are expected to admit 150,000 individual patients II) mean all-cause mortality is 2.9% with variations as described on p. 11, III) a variation in mortality of 25% over the course of the year. The non-inferiority margin is set at 0.5%, and if the intervention has an effect of 0, the study has above 90% power to confirm noninferiority. In a previous cohort of 103,733 patients the mean (SD) number of scores per patient per day was 2.3 (2.0) and 15.4% of patients had one NEWS score of ≥ 6 . With the expected

inclusion, we will be able to detect a difference of 0.04 in mean number of scores and a difference of 0.6% in the number of patients with one NEWS \geq 6 with a power > 90%.

Study end

The follow-up for all patients ends after at total study period of 13 Months and is expected to end at the October 31, 2019.

Statistical plan for main outcome paper

Statistical analyses will be performed using SAS and R. Reporting of results will be in accordance with the CONSORT criteria with extension to cluster randomised trials. Analyses will be done using R. P < 0.05 will be considered statistically significant.

Consort diagram

A modified CONSORT trial profile will be used to describe patient flow and total number patients in each group and at each cluster. All patients not included in analysis will be explained.

Baseline description of groups:

Table of summary statistics for patients and at hospital or cluster level for each group (intervention or control) will be presented with baseline variables (Number of patients, number of admissions, age, sex, Charlson Comorbidity index, hospital characteristics) Continuous variables will be summarized with: n (based on non-missing sample size), mean, standard deviation, median, interquartile range, number of missing values. Categorical variables will be reported as frequency and percentages (based on non-missing sample size) and number of missing values. Continuous and ordinal variables will be tested by Wilcoxon analysis or t-tests as appropriate for differences between groups. Categorical variables will be tested with chi-square.

Primary outcome analysis

The primary outcomes will be an **analysis of all-cause mortality and NEWS/I-EWS scores per patient per day between the intervention and control group**. Patients will be followed as one cohort and data will be analysed as randomized and in accordance with the intention-to-treat principle.

Inclusion: Patients will be included at the first admission at the participating hospitals in the study period (index admission) and will remain in this group (intervention/control) for follow-up of 30 days. Admission is defined as a contact to a hospital with a duration of more than 24 hours. All subsequent admissions (readmission) will be ignored. Any patient lost to follow-up will be censored at the last time known to be alive.

The main analysis of the primary outcome for motality will be done using logistic regression that accounts for clustering with adjustment for hospital ID, age, and sex. Intraclass correlation

coefficient with 95% confidence intervals will be reported. Results will be presented at the individual patient level. Assessment of cluster-level differences will be performed. NEWS/I-EWS scores per patient per day will be compared using linear regressions.

Each period will start with 14 days of implementation, and before cross-over patients will be followed by an observation period of 30 days Periods of implementation and observation will be censored in the analyses (patients admitted in these periods will not be included in the analyses). Cumulative incidence plots (1-survival) will be calculated using the Kaplan-Meier method and presented.

Sensitivity analyses of the primary endpoint

In addition to the ITT analysis, a per-protocol analysis will be performed. In this analysis, interventional patients with missing or incomplete (missing a I-EWS modification in more than 1/3 of the total number of measurements) I-EWS measurement will be excluded. Finally, a sensitivity analysis will be performed, where patients that are transferred between hospitals will be excluded. Sensitivity analyses will be performed for the last three months of each intervention period and excluding departments where I-EWS protocol was not followed.

Subgroup analyses of primary endpoint

The primary outcomes will be calculated for the following subgroups, including a test for interactions: Age (\leq 39 years, 40 to 69 years, \geq 70 years), admissions at defined cluster, and according to the primary discharge diagnosis; cardiovascular disease, infections, pulmonary disease neurological disease, cancer and surgery done during admission. Results will be presented graphically using a forest plot.

Secondary endpoints

Secondary endpoints regarding mortality will be analysed using the same analysis as the primary endpoint. Length of hospital stay between groups will be compared by linear regression following the same adjustment principles as for the primary outcome.

Additional measurements

The frequency of changes in I-EWS that led to an escalation or de-escalation in the escalation protocol will be reported. Changes in NEWS due to CROS values and changes in I-EWS due to clinical assessment will be compared using Poisson regression models.

Handling of missing data

The primary outcome analysis should be subject to no or little missing data as it is based on Danish register data. Patients lost to follow-up (tourists) will be censored at the last registration.

Handling of diagnoses for outcome and subgroups

Diagnoses obtained from the National Patient Registry are coded with the ICD-10 system. The original chapters will be used to group patients according to diagnoses. The primary diagnosis will be used when constructing. The following will define the subgroups: **Cancer:** Chapter II: Neoplasms (C00-C97 + D37-D48). **Cardiovascular disease:** Chapter IX: Diseases of the circulatory system (I09-I52 + I70-I89)

Pulmonary disease: Chapter X: (DJ00-DJ99)

Infections: Chapter I: (A00-B99 + J00-J22 + N10-N11+ N30-N31 + G00-G09)

Neurological disease: Chapter VI: Diseases of the nervous system (G09-G47 + I60-I69)

Surgical conditions: Presence of surgical procedure codes divided into different specialties (general, orthopedic, other)

Hospital	Unique admission in 2016	Death within 30 days
Herlev & Gentofte Hospital (2 units)	41.420	1122 (2.64 %)
Amager & Hvidovre Hospital (2 unit)	26.466	833 (3.05 %)
Nordsjællands Hospital (2 units)	34.159	872 (2.49 %)
Bispebjerg Hospital (1 unit)	13.013	480 (3.55 %)
Glostrup Hospital (1 unit)	6.598	181 (2.67 %)
Sjællands Universitetshospital (2 units)	34.125	845 (2.42 %)
Holbæk Hospital (1 unit)	16.125	531 (3.19 %)
Slagelse Hospital (1 unit)	17.999	705 (3.77 %)
I alt	189.922	5.569 (2,9 %)

Number of unique admissions is based on the wards that are expected to participate in the study.

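### Inclusion depends on a realised stay of more than 24 hours, so first-day deaths drop out of every mortality endpoint and no sensitivity analysis restores them

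*SAP*

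**What the plan says.** The SAP's patient inclusion criteria list "Admittance for more than 24 hours". The section on the primary outcome analysis shows that this is realised rather than expected duration: "Admission is defined as a contact to a hospital with a duration of more than 24 hours". The same section says that "data will be analysed as randomized and in accordance with the intention-to-treat principle".

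The Introduction describes when the scoring starts: "At admission, and as a minimum twice a day, nurses measure vital signs on all hospitalized patients". It gives the purpose of the system as to "prevent serious adverse events like unanticipated transfer to the intensive care unit, cardiac arrest and unexpected death".

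Under Endpoints, the primary endpoint is "All-cause mortality at 30 days". The secondary endpoints include "All-cause mortality at 2 days", mortality at 7 days and length of hospital stay. Follow-up is tied to the index admission, but no time zero is given for the mortality endpoints.

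The section on sensitivity analyses lists a per-protocol analysis, the exclusion of transferred patients, a restriction to the last three months of each intervention period, and the exclusion of departments that did not follow the I-EWS protocol. None of these brings back stays of 24 hours or less.

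**The concern.** Whether a stay passes 24 hours is known only after the hospital has been allocated to its arm and after the arm's scoring system has been used on the patient. The rule therefore selects on something that happens after exposure. Two consequences follow.

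- **Unseen early harm.** A patient who dies on the first day is never included. The score exists to catch early deterioration, and the Ethics section of the short protocol acknowledges a risk that critical illness is overlooked when observation frequency can be adjusted individually. In a non-inferiority comparison, harm that is not counted favours the new system.
- **Possible imbalance.** If I-EWS changed how many patients leave within 24 hours, the included patients in the two arms would differ in risk, and mortality would differ without any true effect on it.

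**Working it through.** The plan gives no figure for this point, so there is none to reproduce. The argument rests on the order of events; the arithmetic only shows scale.

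**Order of events.** (1) The hospital is randomised to a sequence. (2) The patient arrives and is scored at admission, then at least twice a day. (3) The contact ends before 24 hours, by death, discharge or otherwise, or it passes 24 hours. (4) Only in the second case is the patient included. Step 4 depends on step 3, which comes after exposure in step 2.

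**What the mortality endpoints lose.** If days are counted from admission, 2-day mortality in the included set covers hours 24 to 48. If they are counted from hour 24, it covers hours 24 to 72. First-day deaths are absent on both readings, and likewise from 7-day and 30-day mortality.

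**Scale of uncounted first-day deaths.** From the sample size section: 30-day mortality 2.9%, margin 0.5 points, 150,000 patients. *Assumed*: the share f of 30-day deaths that fall in the first 24 hours, with 2.9% taken to include them. The SAP does not say whether its 2016 mortality figures cover short stays.

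Mortality removed = 2.9 × f; deaths per 150,000 = 150,000 × 0.029 × f.

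| f (assumed) | points removed | deaths per 150,000 |
|---|---|---|
| 2% | 0.058 | 87 |
| 5% | 0.145 | 218 |
| 10% | 0.290 | 435 |
| 15% | 0.435 | 652 |

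If I-EWS raised first-day mortality by an assumed relative 25% to 100%, the unseen difference would run from 0.058 × 0.25 = 0.015 points to 0.435 × 1.00 = 0.435 points.

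**Scale of a shift in short stays.** *Assumed*: 2.9% mortality in the more-than-24-hour set, a fraction x of that set moved below 24 hours in the I-EWS arm only, zero mortality in those moved, and no true effect on death.

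Change = 2.9/(1 − x) − 2.9.

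| x (assumed) | change in points | share of 0.5-point margin |
|---|---|---|
| 2% | 2.959 − 2.9 = 0.06 | 12% |
| 5% | 3.053 − 2.9 = 0.15 | 31% |
| 10% | 3.222 − 2.9 = 0.32 | 64% |

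This makes I-EWS look worse. In the opposite case, where I-EWS keeps an extra fraction x of such patients beyond 24 hours, the change is 2.9/(1 + x) − 2.9, that is −0.06, −0.14 or −0.26 points, which would favour I-EWS.

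**Relaxing zero mortality.** *Assumed*: a share s of 20% to 40% of all control contacts already at or below 24 hours, and I-EWS moving a further 2% to 10% of all contacts, with mortality q of 0.2% to 1.0%. Included mortality in the I-EWS arm is [(1 − s) × 2.9% − x × q] / (1 − s − x). The smallest rise is (0.8 × 0.029 − 0.02 × 0.01)/0.78 − 0.029 = 0.05 points. The largest is (0.6 × 0.029 − 0.10 × 0.002)/0.50 − 0.029 = 0.54 points.

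**The case against.** Several points can fairly be made for the plan.

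- **The rule is the same in both arms, and patients are analysed in their allocated arm.** This stands. A reader might infer that the rule contradicts the stated intention-to-treat principle. The text does not support that: no one is analysed in the wrong arm, and what remains is potential selection after allocation.
- **No mechanism for earlier discharge is described.** The escalation protocol is unchanged, and the SAP speaks of measurement frequency and clinical actions, not discharge. This stands too, and it makes the larger shifts speculative. It does not answer the loss of first-day deaths, which needs no change in discharge.
- **The quantified discharge scenario works against I-EWS.** That is correct: it would cost power rather than give false reassurance. The opposite shift and the uncounted deaths run the other way.
- **A do-not-resuscitate order already removes patients from further analysis once it is registered.** Some first-day deaths could be lost by that route anyway, but not all.
- **The CONSORT profile will account for patients not analysed, by group and cluster.** This could reveal unequal exclusion. It does not commit the trial to comparing first-day deaths by arm.
- **Dropping the rule altogether has its own cost.** The margin is absolute. If, as an assumption, 30% of a wider set were short stays with no arm difference, a true 0.5-point harm in the longer stays would appear as 0.7 × 0.5 = 0.35 points. This stands, and it is a good reason not to replace the primary set.

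**Conclusion.** The point holds in a limited form. Eligibility is fixed by realised stay after exposure has begun, first-day deaths cannot be counted in any mortality endpoint, and no planned analysis restores them. That much follows from the text alone.

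Size and direction do not. The illustrative rises of 0.06, 0.15 and 0.32 points, and all the other ranges, rest on assumed shares and risks. They show that an effect could be material beside a 0.5-point margin, not that one exists. A reader might take the result to be biased towards non-inferiority; the document does not establish that.

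A reader might also conclude that 2-day mortality is simply death between 24 and 48 hours. That requires days to be counted from admission, which is the natural reading but is not stated. The listed follow-up data also give a date of death without a time, unlike admission and discharge. The supportable statement is that first-day deaths are excluded and that time zero needs defining.

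**What to change.** Keep the more-than-24-hour set as primary and add three things to the SAP:

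1. A named sensitivity analysis of 30-day, 7-day and 2-day mortality in all otherwise eligible first admissions in the inclusion windows, counted from admission regardless of realised stay. The index contact must be redefined for this analysis, since for some patients it will be an earlier, shorter one.
2. A table by arm of the number of contacts of 24 hours or less and the deaths among them.
3. A stated time zero for the mortality endpoints, with a note that 2-day mortality in the primary set excludes first-day deaths.

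The cost is a wider extract from sources already used (admission and discharge times and date of death are on the data list) and one more analysis. Low-risk short stays will lower its event rate and can dilute the absolute difference, so it should be read beside the primary result and not in place of it.

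### Exclusion criterion 2 most naturally covers DNR and no-EWS orders made after inclusion, which conflicts with the intention-to-treat mortality analysis; the SAP must say which orders count and how such patients are analysed

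*SAP*

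**What the plan says.** Under Exclusion, criterion 2 of the SAP states that once a do-not-resuscitate (DNR) order or a no-EWS registration is identified, "patients will be excluded for further analysis at the time of registration". The inclusion text just above keeps each patient in the arm of the index admission through 30 days.

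Under Primary outcome analysis, "data will be analysed as randomized and in accordance with the intention-to-treat principle", and "The main analysis of the primary outcome for motality will be done using logistic regression that accounts for clustering". Individual censoring is mentioned only for loss to follow-up: "Any patient lost to follow-up will be censored at the last time known to be alive" in that section, and "Patients lost to follow-up (tourists) will be censored at the last registration" under Handling of missing data.

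Under Sensitivity analyses, "In addition to the ITT analysis, a per-protocol analysis will be performed". The other analyses there concern inter-hospital transfers, the last three months of each period, and departments that did not follow the I-EWS protocol. None restores patients removed under criterion 2.

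Under Study variables, the data for included patients contain "Presence of Do Not Resuscitate (DNR) order" and the corresponding no-EWS field. No time of the order is listed.

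**The concern.** An order made during the stay comes after exposure to the assigned scoring system. Its frequency, and how closely it tracks impending death, could therefore differ between arms. The cross-over balances hospitals; it does not balance decisions taken after exposure.

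Patients given such an order may well be at high risk of dying. Dropping them would take deaths out of the endpoint on which non-inferiority is declared, in a trial whose ethics section itself names the risk of overlooking critical illness.

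The rule is also not operational. Dropping the patient, censoring at the order, or ignoring only later scores would give different results, and the SAP does not choose. The CONSORT profile would show unequal removal but would not correct it.

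**Working it through.** **1. Which reading fits the text.**
- Criterion 1 is worded for arrival; criterion 2 is tied to the moment an order is registered and speaks of further analysis. That describes an event in a course already under way.
- DNR status is collected on patients already included.
- The cardiac-arrest definition under Endpoints restricts itself to patients without such an order, which would be largely redundant if none were in the cohort.

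These points favour the in-stay reading but do not prove it.

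**2. The plan's own figure.** Inputs from Sample size calculation: mortality 2.9%, margin 0.5% (taken as percentage points), 150,000 patients. With 1:1 allocation, N = 75,000 per arm. One-sided 0.025 is assumed, because the SAP does not give the sidedness.

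SE = √(2 × 0.029 × 0.971 / 75,000) = 0.0867 points. Power = Φ(0.5/0.0867 − 1.96) > 99%, so the stated figure of above 90% is reproduced. With an assumed design effect (DE) of 3, power is 91%.

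**3. Formula for removal.** Let q be the share of deaths removed and s the share of survivors removed in an arm with true risk P. Patients are dropped, not counted as alive.

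- Deaths kept: d = N·P·(1 − q). Survivors kept: v = N·(1 − P)·(1 − s). Observed risk: p = d/(d + v).
- With R = (1 − q)/(1 − s), observed OR = true OR × R(I-EWS)/R(control).
- P(non-inferiority) = Φ((0.5 − RD)/SE − 1.96), with RD and SE in points and SE² = DE × [p₀(1 − p₀)/n₀ + p₁(1 − p₁)/n₁].

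The odds ratio is therefore biased when R differs between arms. Unequal removal alone is not enough: with 30% of both deaths and survivors removed in control and 20% of both under I-EWS, R = 1 in each arm, RD = 0 and OR = 1.

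**4. Illustrations.** All shares are assumed; s = 5% in both arms. Results with DE 3 are in brackets.

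*No true effect (2.9% in both arms; 2,175 deaths and 72,825 survivors per arm before removal).* Survivors kept: 72,825 × 0.95 = 69,184.
- 30% of deaths removed in control, 20% under I-EWS: deaths kept 1,522.5 and 1,740; risks 2.153% and 2.453%; RD +0.30; OR 0.8/0.7 = 1.14. SE is 0.0797, so power = Φ(0.200/0.0797 − 1.96) = 71% (30%).
- 30% against 28%: deaths kept 1,522.5 and 1,566; RD +0.06; OR 0.72/0.70 = 1.03; power > 99% (about 90%, against 91% with no removal).
- An RD equal to the whole margin needs a gap of about 17 percentage points in deaths removed.

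*True risks 2.9% and 3.4% (RD 0.50, OR 1.18), where non-inferiority should be declared in 2.5% of trials.*
- 20% of deaths removed in control, 30% under I-EWS: RD +0.08, OR 1.03; non-inferiority declared in > 99% (84%). Against an OR margin of 1.178, which corresponds to 3.4% against 2.9%, it is 97% (62%).
- 30% of deaths removed in both arms: OR stays 1.18, but RD shrinks to 0.375 and non-inferiority is declared in 34% (14%) on the risk-difference scale.
- The excess deaths carry no order: 652.5 deaths are removed in each arm, which is 30% of 2,175 but 25.6% of 2,550. This is unequal removal. RD rises to 0.53 (0.56 with s = 10%), OR is about 1.25, and non-inferiority is declared in at most 1.5%.

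**The case against.** The sentence stands under patient exclusion criteria and could be an ordinary baseline criterion, with registration meaning registration of the patient. Then there is no intention-to-treat conflict. A reader might infer that the SAP definitely commits to dropping patients for in-stay orders; the wording leans that way but does not settle it. What stands is that the text leaves both timing and handling open. A third reading, that only data after the order are unused, has no place in a logistic model of 30-day death, and such censoring in the Kaplan-Meier plots would probably be informative.

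A reader might also infer that any difference between arms in removal biases the result. It does not: bias depends on the retention ratio R, and equal shares of deaths and survivors within each arm leave the risks unchanged.

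Finally, every removal share above is assumed, and the large effects need a gap of about 10 points in deaths removed. Each hospital supplies both arms and hospital is adjusted for, so stable differences in order practice should largely cancel. This stands as a limit on the likely size. It does not exclude an effect of the intervention, or of period, on orders.

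**Conclusion.** The concern holds in conditional form. On its most natural reading, criterion 2 removes included patients for an event after exposure. That contradicts both the 30-day retention rule and the as-randomised analysis, and it leaves the primary model without a defined way to handle them. On the baseline reading the defect is one of wording only.

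If in-stay orders count, mortality is biased whenever the ratio of deaths retained to survivors retained differs between arms, in either direction. Equal removal that is selective for deaths leaves the odds ratio alone but shrinks a true risk difference against the fixed 0.5-point margin. The SAP does not say on which scale the margin is tested.

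The SAP does not support a claim that the trial is biased towards non-inferiority, or by any particular amount, because it gives no order rates, timing or split by arm. The illustrations run from negligible (a 2-point gap) to decisive (a 10-point gap). They rest on the assumed shares, 75,000 per arm, one-sided 0.025 and, where stated, a design effect of 3. Because the primary safety conclusion is at stake and the remedy is wording, it should be fixed.

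**What to change.** - Keep every included patient in the 2-, 7- and 30-day intention-to-treat mortality analyses, whatever orders come later.
- Limit order-based exclusion to orders in force at index admission, applied identically in both arms. State that orders made after admission do not exclude. This includes orders in the first 24 hours, which need explicit mention because inclusion requires a stay of more than 24 hours.
- For the scores-per-patient-per-day endpoint only, stop counting both scores and days at the order.
- Report the number of orders by arm and period.
- Keep the current rule as a named sensitivity analysis that states whether patients are dropped or censored.

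The cost is SAP wording. Dates of death are already collected at follow-up, so no new outcome data are needed. The availability of order times must be confirmed, because only the presence of each order is listed. The drawback is that patients whose care the score no longer influences stay in the intention-to-treat set. That slightly dilutes a true difference, which matters in a non-inferiority trial; the sensitivity analysis addresses it.
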